For treatment delivery, subjects will be asked to sit on the device and the height will be adjusted until the subject's feet are on the floor. The active treatments are individualized, since some subjects will be more sensitive than others, and thresholds may vary from visit to visit. The Emsella Chair will be turned on and the setting gradually increased to the subject's sensory threshold; the maximum sensation the subject can tolerate, with the goal of a minimum 50% setting. The subject will not be left unattended throughout the treatment session. The treatment threshold should be increased with every treatment until the subject reaches 100%.

Sham subjects will be positioned on the device in the same manner. The sham treatment will provide some sensation without active HIFEM technology. The programming for the sham treatment will have an amplitude limitation, with the setting below therapeutic level (<10% power).

Regardless of group assignment, each treatment is \leq approximately 28 minutes at which time the device automatically shuts off. If at any time point, there are two treatment visits where the subject cannot tolerate a setting of at least 50%, they will be withdrawn from the study at the second occurrence. If a subject cannot endure the entire treatment duration, they will be withdrawn from the study.

The primary endpoint for follow up evaluation will be 4 weeks after completion of the last treatment (week 8 of the study). The durability endpoint is 4 weeks following the primary endpoint (week 12 of the study).

At each clinic visit, study procedures will be performed as specified in the table of events, located in Appendix A.

Study subjects will not be compensated for their participation in the trial. However, all research related activities, specified on the table of events, will be provided at no cost to the study subject.

TREATMENT ALGORITHM

Emsella Chair (2 times/week for 4 weeks)	Sham Emsella (2 times/week for 4 weeks)
--	---

Treatment Group Assignment

Subjects meeting all eligibility criteria will be randomized to the active treatment group or sham in a 1:1 ratio.

RANDOMIZATION and BLINDING

The study will be performed in a single-blind manner (subject and biostatistician will be blinded to treatment). Subjects will be randomized 1:1 to active Emsella Chair treatment or sham treatment. Subjects will be enrolled in the study and randomized:

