Subjects will return 2 times per week for Emsella Chair or sham treatments for 4 consecutive weeks. Treatments will ideally be delivered at least 2 days apart from one another. Should scheduling challenges occur, the goal will be to complete all 8 treatment visits within a 6-week window. Prior to conducting the first treatment each week a urine pregnancy test (if applicable) will be performed. If the urine pregnancy test is positive, the subject will be withdrawn from the study. VAS-pain will be completed by subject pre- and post each treatment visit. Additionally, before each second weekly treatment visit, the subject will complete the PGI-I and PGI-S. At visit 8, the subject will complete a treatment blinding assessment, indicating if they believe they received active or sham treatment. Concomitant medications and adverse events will be reviewed and changes from the previous visit will be recorded.

If at any time a patient reports a fever, an oral temperature will be obtained. If a fever, defined as $\geq 38^{\circ}$ Celsius, is present, treatment will be delayed until the fever is resolved at a later visit.

Urine dipstick will not routinely be collected for analysis at the study treatment visits. However, as standard of care, if UTI symptoms are reported by the subject, urinalysis via dipstick will be performed. If positive for leukocytes, a urine culture will be sent, and the subject will be treated appropriately. Subjects will be allowed to continue study treatments if they are being treated for a UTI, unless they have a fever, defined as temperature $\geq 38^{\circ}$ Celsius.

Follow-up Visits

Visit 9, Week 8, Primary Endpoint

Approximately 4 weeks after finishing treatment, the subject will return to the study site for a clinic visit. A dipstick urinalysis will be performed. If positive for leukocytes, a urine culture will be sent. If the subject has a confirmed symptomatic UTI, per investigator's clinical judgment, the remaining activities for this visit will be postponed until treatment is completed and symptoms have resolved. The subject will complete the VAS, PGI-I, PGI-S, FSFI (females only) or BSFI (males only), BDI, OAB-q, ICSI-PI, GAD7, MPQ, PCS, and GRA. Concomitant medications and adverse events will be reviewed and changes from the previous visit will be recorded. For female subjects, a gynecologic (female) or digital rectal (male) exam will be completed with palpation of levator muscles for assessment of tenderness.

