Visit 10, Week 12, Secondary Endpoint

Approximately 8 weeks after finishing treatment, the subject will return to the study site for a clinic visit. The subject will complete the VAS, PGI-I, PGI-S, FSFI (females only) or BSFI (males only), BDI, OAB-q, ICSI-PI, GAD7, MPQ, PCS, and GRA. Concomitant medications and adverse events will be reviewed and changes from the previous visit will be recorded.

After completing all visit activities, the subject will be unblinded to treatment group. If subjects were in the sham group, they will be offered the opportunity to receive Emsella Chair treatments. Subjects choosing to continue in the study will follow the same active treatment protocol and follow the schedule of activities for Visits 1-10, specified in Appendix A.

SUBJECT DISCONTINUATION OR WITHDRAWAL

Subjects are free to discontinue study participation at any time upon request. Subjects who discontinue study treatment or active participation in the study will no longer receive treatment with Emsella Chair or sham. When a subject withdraws from the study, the reason(s) for withdrawal shall be recorded. Every effort will be made to obtain all end-of-treatment measures.

Additionally, subjects may be withdrawn from the study by the Principal Investigator (PI) for any of the following reasons:

- Subject cannot complete the full duration of treatment
- Subject cannot tolerate a minimum treatment level of 50% at any two treatment visits
- Development of any condition or AE that are clinically significant and may pose an additional risk to the subject
- The PI decides is in the best interest of the subject to withdraw from the study
- Subject is unable to follow Investigators' instructions and/or to comply with the study protocol

Replacements

Subjects who have been randomly assigned to receive treatment and who subsequently discontinue prematurely from the study may be replaced by another subject. The goal is to have 60 patients complete the entire study; 30 patients in each arm. Therefore, if/when subjects withdraw from the study prior to completing visit 9, an additional subject will be enrolled. Each subject will be assigned their own unique study identification number.

Subjects who fail to satisfy inclusion and exclusion criteria at screening may be rescreened at the discretion of the PI.

TABLE OF EVENTS

The table of events is included in Appendix A.

RISKS AND BENEFITS

Possible Risks

- Worsening of CPP
- Muscular pain
- Temporary muscle spasm

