APPENDIX A

Table of Events

Visit	Screening		Week 1		Week 2		Week 3		Week 4		Week 8 ^g		Week 12		Week 13		Week 14		Week 15		Week 16		Week 17		Week 18		Week 19		Week 20		Week 24						
	0		1	2	3	4	5	6	7	8	9	10	11	12	13	14	15	16	17	18	19	20	21	22	23	24	25	26	27	28	29	30					
Visit Window ^a			±14 days								±7 days																										
Informed consent	X																																				
Eligibility criteria review	X	X																																			
Medical history & Demographics	X																																				
Height and weight	X																																				
Urine pregnancy test ^b	X	X	X						X																												
UA dipstick (with culture as needed) ^c	X									X																											
Gynecologic Pelvic examination ^d	X									X																											
Digital rectal examination ^e	X									X																											
Randomization			X																																		
Treatment: Emsella or Sham			X	X	X	X	X	X	X																												
Blinding assessment									X																												
Pain VAS	X										X																										
Pain VAS pre/post treatment			X	X	X	X	X	X	X																												
PGI-I			X	X	X	X	X	X	X																												
PGI-S	X		X						X																												
FSFI (females), BSFI (males), BDI, OAB-q, ICSI-PI, GAD7, MPQ, PCS	X									X																											
GRA										X																											
Concomitant medications	X		X	X	X	X	X	X	X																												
Adverse event(s)			X	X	X	X	X	X	X																												
Un-blinding (Sham group is offered active treatment after un-blinding) ^f														X																							

^a Visit windows may be extended due to scheduling challenges, with the goal of completing all 8 treatment visits within a 6-week window.

^b Only women of child-bearing potential will be required to have a urine pregnancy test

^c UA and C&S may be repeated if the patient is symptomatic at any other time during visits 1-8, per clinician judgment

^d Female patients will undergo a gynecologic pelvic examination to assess levator muscle tenderness

^e Male patients will undergo a digital rectal examination to assess levator muscle tenderness

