^fPatients that are originally randomized to the sham treatment will be offered active treatment after the secondary endpoint visit is completed. Those patients who wish to undergo active treatment will then follow the same schedule of events as above, for visits 1-10, except for the validation of blinding questionnaire.

^gThe primary endpoint for follow up evaluation will be 4 weeks after completion of the last treatment (week 8 of the study). The durability endpoint is 4 weeks following the primary endpoint (week 12 of the study).

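### A confirmed symptomatic UTI postpones the screening and Week 8 assessments but not the Week 12 durability assessments, which cannot be repeated under the blind

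*Combined protocol and SAP*

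**What the plan says.** **UTI handling at the assessments that define baseline, Week 8 and Week 12**

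- *Screening: Visit 0* and exclusion criterion 4: a confirmed symptomatic UTI, in the investigator's judgment, defers screening until it has been treated and symptoms are gone.
- *Visit 9, Week 8, Primary Endpoint*: a dipstick is done, with culture if positive for leukocytes. With a confirmed symptomatic UTI, "the remaining activities for this visit will be postponed until treatment is completed and symptoms have resolved". No maximum delay is given.
- *Visit 10, Week 12, Secondary Endpoint*: the text goes straight to the VAS and the same questionnaires, with no dipstick and no postponement. When the visit's activities are complete the subject is unblinded, and sham subjects are offered active treatment.
- Appendix A footnote c: urinalysis and culture may be repeated for symptoms during visits 1-8. Visit 10 is not mentioned.

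**Timing of the two follow-up visits**

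- Visit 9: "Approximately 4 weeks after finishing treatment, the subject will return to the study site for a clinic visit".
- Visit 10: "Approximately 8 weeks after finishing treatment, the subject will return to the study site for a clinic visit".
- *Endpoints*, *Methodology* and footnote g also call these Week 8 and Week 12, which fits the planned four-week course. For slower schedulers, however, "the goal will be to complete all 8 treatment visits within a 6-week window".

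Under *Analysis Sets*, the durability set is everyone who received all eight treatments and completed the 12-week visit, with no condition on when that visit took place.

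**The concern.** The protocol treats a symptomatic UTI as a reason not to take the baseline or Week 8 assessments. It gives no reason for treating Week 12 differently. The instruments are the same, and some are directly exposed: Appendix B describes the ICSI-PI as measuring urinary and pain symptoms, and the OAB-q covers urgency and frequency.

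Week 12 carries the durability objective, which asks whether the active group still has less pain than sham four weeks after the primary endpoint. Pain from a UTI on that day can look like loss of benefit in a subject whose Week 8 reading was protected from the same disturbance. A poor Week 8 reading can be avoided by waiting. A poor Week 12 reading cannot be replaced later, because the subject then knows the allocation and a sham subject may have started active treatment.

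**Working it through.** **1. The plan's own figure, as a yardstick.** Inputs from *Sample Size Calculation*: SD 2.5 cm at baseline and Visit 9, within-subject correlation 0.2, 30 per arm, 80% power, 5% significance. Sidedness is not stated; two-sided is used here.

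- SD of change = 2.5 × √(2 × (1 − 0.2)) = 3.162 cm.
- Detectable difference = (1.9600 + 0.8416) × 3.162 × √(2/30) = 2.287 cm (2.326 cm with the t distribution).

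Both round to the stated 2.3 cm, so the figure is reproduced. Power for 2.3 cm is 80.4% (normal approximation). Using it at Week 12 assumes the same SD, correlation, sample size and significance level there.

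**2. Effect of active UTIs at Visit 10.** The documents give neither a UTI rate nor its effect on VAS, so both are assumed. Let a proportion p of subjects be affected and each gain b cm.

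- Mean shift in each arm = p × b.
- SD of change becomes √(3.162² + b² × p × (1 − p)).

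| p | b (cm) | Mean shift, each arm (cm) | SD (cm) | Power for 2.3 cm |
|---|---|---|---|---|
| 2% | 1 | 0.02 | 3.165 | 80.4% |
| 2% | 3 | 0.06 | 3.190 | 79.7% |
| 5% | 1 | 0.05 | 3.170 | 80.2% |
| 5% | 3 | 0.15 | 3.229 | 78.8% |
| 10% | 3 | 0.30 | 3.288 | 77.3% |

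At p = 3% and b = 3 the shift is 0.09 cm. The 0.09-0.15 cm range is 0.09/2.3 = 4% to 0.15/2.3 = 7% of the detectable difference.

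**3. Where the shift goes.** With the same rule and the same UTI rate in both arms, it adds p × b to the Week 12 mean in each. It cancels in expectation from the difference between arms and appears as a time effect, resembling waning from Week 8 to Week 12. What remains in the contrast is chance imbalance: one extra affected subject among 30, at +3 cm, moves that arm's mean by 3/30 = 0.10 cm.

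**4. How likely it is to arise.** The chance of at least one affected subject among 60 is 1 − (1 − p)^60: 70% at p = 2% and 95% at p = 5%.

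**5. Timing labels.** With last treatment in Week 4, the week labels and the treatment-based intervals agree. With last treatment in Week 6:

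- timed from treatment, Visits 9 and 10 fall in study Weeks 6 + 4 = 10 and 6 + 8 = 14;
- read as study weeks, they fall 8 − 6 = 2 and 12 − 6 = 6 weeks after treatment.

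If Visit 9 is postponed by d weeks, Visit 10 is 4 − d weeks after it when kept at 8 weeks from treatment, or 8 + d weeks from treatment when counted from the actual Visit 9. For d = 2 (an assumption) that is a 2-week gap, or 10 weeks from treatment.

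**The case against.** A reader might infer something stronger from the timing arithmetic: that the two visits run on conflicting clocks and time since treatment is uncontrolled. The documents do not support that as a defect in itself. The instructions for Visits 9 and 10 both count from the end of treatment. *Endpoints* defines the primary endpoint as a timepoint four weeks after all treatments, and four weeks after that timepoint is eight weeks after treatment, which matches the Visit 10 text. The 2- and 6-week figures arise only if staff follow the nominal labels instead. A wider range built on a ±7-day window cannot be asserted, because the Appendix A table is broken in the available copy and the visit to which that window applies cannot be read. What stands is that the labels are loose when treatment runs past four weeks, and that a sentence on Visit 10 after a postponed Visit 9 would help.

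On the UTI point there are four fair objections.

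- The rule is identical in both randomized arms, so it does not evidently favour either. This stands.
- Adverse events and concomitant medications are reviewed at Visit 10, so a reported UTI would be on record, and the separate SAP could address it. This helps identify affected readings but cannot recover a clean blinded one.
- The broken table cannot prove that no Visit 10 dipstick is scheduled. This stands; the point rests on the Visit 10 text and footnote c. Even a scheduled dipstick would not supply the missing postponement.
- Treatment-visit VAS scores are not protected either, since *Study Treatments* allows treatment to continue during a UTI without fever. True, but the comparison at issue is between baseline, Week 8 and Week 12, and only the last of these lacks the safeguard.

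**Conclusion.** The UTI asymmetry is real and worth correcting. As written, Week 12 VAS, ICSI-PI and OAB-q can be collected during an active UTI that would have postponed the same instruments at screening or Week 8, and unblinding then rules out a blinded repeat.

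The consequence is modest. Over the assumed ranges (2-10% affected, 1-3 cm each) mean VAS rises 0.02-0.30 cm in each arm, and power for 2.3 cm falls from 80.4% to 77.3% at worst. The working range of 0.09-0.15 cm assumes 3-5% affected and 3 cm each. None of these rates or effects comes from the documents.

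A reader might also infer a bias between active and sham. Nothing in the documents points to one, because the rule and the follow-up schedule are the same in both arms. The loss is precision and a clean Week 8 versus Week 12 comparison. The timing labels need clarification only.

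**What to change.** 1. In the Visit 10 text, ask about UTI symptoms on arrival. If a symptomatic UTI is confirmed, postpone the VAS and questionnaires on the terms already used at Visit 9, and keep unblinding until after the postponed assessments. Extend footnote c so that symptom-triggered urinalysis covers Visit 10. Treatment of the UTI is not affected.
2. State a maximum delay for the postponement at both Visit 9 and Visit 10; at present Visit 9 has none.
3. In the SAP, define the assessment window for each visit and add a sensitivity analysis excluding off-window readings. The durability set currently has no timing condition.
4. As a clarification, state once that Visits 9 and 10 are timed 4 and 8 weeks from the subject's last treatment, as the visit text already says; that Week 8 and Week 12 are nominal labels when treatment runs past four weeks; and that Visit 10 stays on that clock if Visit 9 is postponed. Align *Endpoints*, *Methodology*, *Methods* and footnote g with this. Keeping Visit 10 fixed shortens its interval from a late Visit 9; the sensitivity analysis in item 3 covers that.

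The cost is wording in a few sections and one added analysis, with no new visits. A few Week 12 readings will be late, and for those subjects unblinding, and the offer of active treatment to sham subjects, will be late as well.

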Durability of the treatment effect will be examined in the DS for this efficacy endpoint.

Missing Data

We will use complete case analysis for all efficacy endpoints as long as the percent of missing data is less than 5%. If the proportion of missing data is greater than 5%, we will evaluate the potential missing data mechanism including examining associations between baseline characteristics and the probability of missing. Importantly, we will examine if dropout rates differ between the groups, as well as whether dropout is related to baseline patient reported pain and discomfort VAS score. Provided there is no evidence for data being missing not at random, we will use multiple imputation for all missing data. In this scenario, responder status will be based on the imputed patient reported pain and discomfort VAS score at Week 8.

Safety Analyses

All safety parameters (including AEs) will be summarized using the SA set. No formal hypothesis testing will be performed.

All AEs will be coded using the latest version of MedDRA. All treatment emergent adverse events (TEAEs) will be summarized and presented in the listings by the number of subjects reporting an event, the percentage of subjects with that event, the number of events, and the grade, duration, and relationship to treatment. Percentages will be based on the number of subjects who received each treatment during the study. TEAEs are defined as events that

emerge during treatment, having been absent pretreatment, or worsen relative to the pretreatment state.

DATA and SAFETY MONITORING PLAN

Ongoing safety monitoring will be performed by the study staff, including the Principal Investigator (PI) and co-investigators. The PI will have ultimate responsibility of assuring subject safety. Safety issues will also be addressed in the annual reports to Beaumont's Investigational Review Board (IRB).

Additional data safety monitoring procedures include:

- Research Administration's Clinical Research Quality and Process Improvement Program (CRQIP) will perform in-house monitoring of the first subject enrolled after the completion of Visit 1
- An audit of the study records after the first 10 subjects are enrolled, at the halfway point of enrollment, and at the end of the study by an RN in the Urology Research Department that is not directly involved with the research study. Additional monitoring may occur as needed. This will be done to ensure the safety of subjects and lack of significant adverse effects.

As an on-going plan, any adverse effects (prolonged irritation, hemodynamic changes, significantly worsened pain, or other deemed significant by clinicians) will be reported to the study staff and then to the PI at the time of the event. Adverse events, serious adverse events, and unanticipated problems not listed in the risks section of this protocol will be reported per IRB guidelines.

Subject records will be reviewed to verify case report form (CRF) completion and delinquencies, and capture protocol deviations and frequency of unanticipated problems/adverse events. To identify, evaluate, and prevent adverse events, the total number of events will be reviewed, as well as the details of each event, including visit number and severity. Data will be reviewed to identify trends and possible concerns. Enrollment data will direct recruitment efforts and assist in study planning.

The overall objectives of routine monitoring are to:

- Document clinical study progress.
- Document that the protocol and associated forms are current.
- Obtain and review current clinical data, reports, and source documents.
- Review the overall study status including verification of the study files. All required documents and records should be accurate, complete, and current.
- Confirm that all subjects have signed the informed consent form.
- Confirm that all enrolled subjects have met the eligibility criteria.
- Verify accuracy of transferring data from source document(s) to the CRFs to the database.
- Confirm complete, accurate, and timely event reporting.
- Confirm adequacy of staff and facilities.
- Review communication records.
- Verify identification and reporting of protocol violations.

Outcomes of all scheduled and unscheduled study monitoring will be documented. Follow-up action items will be included in the report. The monitoring summary report will be forwarded to the PI and research coordinator.

Quality Control and Quality Assurance (QC/QA)

The PI or designee has primary responsibility for QC/QA activities of the data. Beaumont's Research Institute also audits investigator-initiated studies to ensure compliance with consent processes and reporting requirements. The key QC/QA activities for the study will be:

- Clearly formatted and carefully constructed CRF;
- Sign-Off Procedures for all CRFs;
- Verification of subject eligibility at each visit

A database will be created utilizing RedCap or MS Excel software. Only designated study personnel will have access to the database, which will be stored on the Urology Research Department's shared drive. Access to the computerized system will be password protected. To ensure accuracy of data entry, database entries will be cross-checked against source documents. The shared drive is backed up nightly to ensure minimal data loss, even in the most catastrophic system failure. The database will be active until all study visits are completed, final monitoring activities have been conducted, and all data queries have been resolved. After that time, the database will be locked, prohibiting any changes to the data.

All study records, including both paper and electronic, will be stored in accordance with all federal and institutional requirements, including, but not limited to, the HIPAA Privacy Rule, the Food and Drug Act, and Medicare policy. The stored data will be kept in a secure, protected manner. All records will be retained, at a minimum, for eleven years beyond study completion.

SUMMARY of EXISTING STUDY DATA

The BTL Emsella has received 510(k) approval as a "nonimplanted electrical continence device" and is currently being used as a non-invasive treatment for SUI. The limited number of studies on this HIFEM technology have focused on its effects on stress, urge, and mixed urinary incontinence as well as quality of life. A white paper, entitled "HIFEM™ Technology Can Improve Quality of Life of Incontinent Patients" summarizes the results of a pilot study, which enrolled and treated 30 women with stress, urge or mixed urge incontinence [29]. Quality of life (QOL) was assessed after the women received 6 treatments, and again at 3 and 6 months post treatment. Ninety-five percent (95%) of the women reported improvement in QOL after treatment completion. Results were maintained over the follow-up periods. Additionally, 67% of the women decreased or eliminated the use of incontinence pads. Similar results were seen in studies by Samuels, Alinsod, Cidranes and Blanco [30, 31, 32, 33]. Additionally, advance ultrasound (elastography) revealed elastographic changes, indicating the improvement in pelvic muscle tone in all the subject's post-treatment.

